5.15.2 Injection Site Reactions

The type of injection site reactions from administration of IMM-101 will be summarised at each administration visit.

A further summary will present the worst reported CTCAE grade for each injection site reaction type which occurred over the entire study period. If a subject experienced more than one reaction within an injection site reaction type, the subject will be counted once at the worst CTCAE grade.

Details of all injection site reactions will be listed.

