#### **7.1.6 Dosing**

IMM-101 is administered as a single 0.1 mL intradermal injection of IMM-101 (10 mg/mL) into the skin overlying the deltoid muscle, with the arm being alternated between each dose. The Investigator will have been appropriately trained *a priori* in the technique of intradermal injection.

Previous clinical experience with IMM-101 has suggested that this dose is well tolerated. The skin reaction that develops at the site of injection is characterised by erythema, local swelling and occasionally mild ulceration. All symptoms are to be expected given the known pharmacology of the product and previous clinical experience. Furthermore, data from safety

Page 43 of 98

and tolerability studies with IMM-101 have revealed that skin reactions resolve satisfactorily over time and do not impair daily activity.

The first dose of IMM-101 administered to each patient in the study is followed by vital signs monitoring for at least 2 hours under medical supervision with resuscitation facilities available as a precautionary measure.

The treatment regimen will be 1 dose of IMM-101 given every 2 weeks for the first 3 doses followed by a rest period of 4 weeks, then one dose every 2 weeks for the next 3 doses. This is followed by a dose every 4 weeks thereafter with a window of  $\pm$ 2 days allowed.

Nivolumab and ipilimumab are administered according to the prescribing information. When either nivolumab or ipilimumab are administered on the same day as IMM-101, according to the Schedule of Assessments, patients will receive IMM-101 first. The first dose of nivolumab administered to each patient on study is given at least 2 hours after the first dose of IMM-101.

The Study Schedule of Assessments is presented in Appendix 1.

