# 8.3 STUDY PROCEDURES: WITHDRAWAL/END OF STUDY VISIT (WEEK 80)

The Study Schedule of Assessments for the Withdrawal/EOS visit is provided in Appendix 1.

When a patient withdraws from or completes the study, where possible the patient should attend an EOS visit. This visit should be within 28±7 days after the final study dose of IMM-101. If an end of study visit is not possible, any unresolved adverse events and update on concomitant medications should be followed up by other means of contact (e.g. telephone; Section 9.5).

The following assessments will be performed: Physical examination (see Section 8.4.2)

- Vital signs (resting blood pressure, pulse, body temperature, and weight; see Section 8.4.5)
- Blood sample for safety laboratory assessment (see Section 8.4.7).
- CT/MRI scan (only required if there is more than 8 weeks elapsed since the last scan or more than 12 weeks elapsed if last scan was after week 52 and only when there is already no documented progression)
- Eastern Cooperative Oncology Group (ECOG)/World Health Organisation (WHO) performance status (see Section 8.4.4)
- 12-lead ECG (See Section 8.4.6)
- Record any concomitant medications/procedures since the last visit (see Section 6.5)
- AE/SAE reporting (see Section 9.2/9.3)
- Solicited and visible injection site reactions (see Section 8.4.10)

For patients completing the study, the last dose of nivolumab is given at Week 76 or 78 (dependent on 2 weekly or 4 weekly dosing regimen). Any patients in Cohort A who are to continue to receive nivolumab off study should have their End of Study visit before any such off-study treatment.

In addition, after patients withdraw from the study, their GP will be contacted for continued collection of survival data and information on subsequent therapy (see Section 6.3).

Page 54 of 98

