### 11.1.1 Methods of Analysis

Descriptive evaluation of the efficacy and safety endpoints will be performed using summary statistics (number of patients [n], mean, standard deviation [StD], median, minimum, maximum) for continuous data endpoints and frequency counts and percentages for categorical data endpoints. Percentages will be calculated using the total patients in the respective analysis set.

All AEs and procedures will be coded using the Medical Dictionary for Regulatory Activities (MedDRA) drug dictionary and all concomitant treatments will be coded using the World Health Organisation (WHO) Drug Dictionary. All patient data will be presented as data listings by cohort.

Exact 95% binomial confidence intervals (CIs) will be calculated for the observed ORR (using RECIST 1.1 and irRC criteria) and disease control rate (cohort B only). Overall survival, PFS, duration of and time to response (RECIST 1.1) will be summarised by Kaplan-Meier (KM) methods and presented graphically where appropriate. The median OS (if applicable) and 1-year OS rate will be estimated for both cohorts.

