- Patient has a tumour sample (archived tissue in the last 3 months or newly obtained biopsy) that is adequate for PD-L1 assessment prior to enrolment. The tumour sample will be collected during screening for PD-L1 expression testing from all patients in Cohort A. Patients will be eligible to participate regardless of the level of PD-L1 expression. Patients with an inadequate archived sample may obtain a new biopsy and patients with an inadequate newly obtained biopsy may undergo re-biopsy at the discretion of the investigator.
- 9 Performed during screening unless patient has documented BRAF status.
- 10 Cohort A Baseline sample for PD-L1 testing is used for baseline immunological testing. Archived tissue collected during the 3 months prior to Screening may be used if available. Samples for Cohort A and Cohort B are subject to consent for immunological testing. Subsequent sample will be scheduled at Week 12 (to be taken in the following 2 weeks) for Cohort A. Subsequent sample requested from Cohort B only if a response to treatment is recorded.
- 11 If IMM-101 and nivolumab are due to be administered on the same day, IMM-101 will be given before nivolumab.
- 12 According to Investigator choice, Nivolumab will be given as 3mg/kg IV infusion every two weeks, 240mg IV infusion every two weeks or 480mg IV infusion every four weeks.
- 13 Injection site reactions are recorded prior to each new injection and at the End of Study visit.
- 14 When a patient withdraws from, or completes, the study, where possible the patient should attend an EOS visit. This visit should be within 28±7 days after the final study dose of IMM-101. If an end of study visit is not possible any unresolved adverse events and update on concomitant medications should be followed up by other means of contact (e.g. telephone; Section 9.5). Patients will then be followed up for survival.
- 15 A CT scan is only required at End of Study visit if there is more than 8 weeks elapsed since the last scan (or more than 12 weeks elapsed if last scan was after week 52) and, in both cases, when there is no documented progression.
- 16 From time of signing informed consent.
- 17 Any patients in Cohort A continuing treatment with nivolumab off-study should have their End of Study visit before they receive this.

Protocol No. IMM-101-015

Final Version 2.0 incorporating Amendment 1, 16 December 2019

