5 ANALYSIS PLAN

5.1 General

Summary statistics for continuous variables will consist of the number of non-missing observations (n), mean, standard deviation (StD), minimum, median and maximum, unless specified otherwise.

For categorical variables the number and percentage of subjects in each category will be presented, based on the number of non-missing observations apart from disposition of subjects, protocol deviations, background and demographic characteristics, prior and concomitant medications/procedures and adverse events where the percentage will be based on the number of subjects in the analysis set, or subgroup of the analysis set, with a missing category presented where applicable. Any exceptions to these are detailed within the table, listing and figure shells.

The mean and median will be displayed to 1 more decimal place than the original data values and the StD will be displayed to 2 more decimal places than the original data values. The minimum and maximum will be displayed to the same number of decimal places as the original data. Percentages will be displayed to 0 decimal places; percentages will not be presented when the count is zero.

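### The by-visit injection site reaction table in SAP 5.15.2 has no place for the End of Study assessment, and the SAP's default percentage base for these reactions departs from the protocol undeclared

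*SAP*

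**What the plan says.** SAP 5.15.2 plans three outputs for injection site reactions.

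- A by-visit table of reaction type: "The type of injection site reactions from administration of IMM-101 will be summarised at each administration visit".
- A worst-grade table: "A further summary will present the worst reported CTCAE grade for each injection site reaction type which occurred over the entire study period". Each subject counts once per reaction type.
- A listing: "Details of all injection site reactions will be listed".

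The assessment schedule is in protocol Appendix 1, note 13: "Injection site reactions are recorded prior to each new injection and at the End of Study visit". Protocol 8.3 places the End of Study visit after dosing has ended: "This visit should be within 28±7 days after the final study dose of IMM-101".

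On percentages, SAP 5.1 states: "For categorical variables the number and percentage of subjects in each category will be presented, based on the number of non-missing observations". A list of exceptions follows. It names adverse events but not injection site reactions, and SAP Table 1 lists the two as separate items. SAP 5.1 also allows the table shells to set further exceptions. Protocol 11.1.1 states a different rule: "Percentages will be calculated using the total patients in the respective analysis set". SAP section 6, which lists changes from the protocol's planned analysis, does not mention the percentage base.

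The incidence and frequency of local injection site reactions is a secondary safety endpoint (protocol 5.2.2, SAP 2.2.2).

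**The concern.** A reaction is looked for before the next injection. After the last injection no further one is given, so the End of Study visit is normally where that reaction is recorded. A table restricted to administration visits has no column for it.

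This matters for the frequency part of the endpoint. The worst-grade table counts a subject once per type, so repeat reactions are tabulated only in the by-visit table. The last dose is also not a random omission: protocol 3.5 says that the incidence and severity of these reactions rise with continued dosing, and a patient may have stopped because of one. The adverse event tables do not fill the gap for milder reactions. Protocol 9.5 makes recording a reaction as an adverse event a matter of investigator judgement, except that those of Grade 3 or higher should be recorded.

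The percentage base raises a second question. If subjects without a reaction have no grade record, a non-missing base turns the worst-grade table into a grade distribution among reactors instead of an incidence among treated patients.

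**Working it through.** The documents give no expected reaction rate and no formal sample size calculation, so there is no planned figure to reproduce.

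**Last-dose assessment**

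Inputs: the IMM-101 regimen in protocol 7.1.6 ("The treatment regimen will be 1 dose of IMM-101 given every 2 weeks for the first 3 doses followed by a rest period", then three more doses two weeks apart, then one every four weeks) and the administration weeks in Appendix 1.

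1. Dose weeks are 0, 2, 4, 8, 10 and 12 (6 doses), then 16 to 76 in steps of 4: (76 − 16)/4 + 1 = 16 doses. Total 6 + 16 = 22.
2. A subject who receives k doses has k post-dose assessments: k − 1 at later administration visits and 1 at End of Study. The share without a column in the by-visit table is 1/k.
3. Results:

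| Doses received | At later administration visits | End of Study only | Share omitted |
|---|---|---|---|
| 22 (completer) | 21 | 1 | 4.5% |
| 6 (stops after Week 12) | 5 | 1 | 16.7% |
| 3 (stops after Week 4) | 2 | 1 | 33.3% |
| 1 | 0 | 1 | 100% |

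4. The rule in SAP 5.4 that safety tables use scheduled data only does not cause the omission, because End of Study is a scheduled visit. The cause is the wording of 5.15.2.
5. The worst-grade table omits nothing: it runs over the whole study, in line with protocol 11.1.4, which takes the worst grade over all assessments.

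**Percentage base**

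Inputs: planned cohort sizes n = 18 (A) and n = 8 (B), from SAP section 3. The number of reactors r and the number of subjects with no record m are assumptions. The comparison is r/(n − m) on the SAP default against r/n under the protocol.

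1. Cohort A, r = 9: 9/18 = 50.0% under the protocol. With m = 1 to 4, the SAP default gives 9/17 = 52.9% to 9/14 = 64.3%.
2. Cohort B, r = 4: 4/8 = 50.0% under the protocol. With m = 1 to 4, the SAP default gives 4/7 = 57.1% to 4/4 = 100%.
3. If subjects with no reaction have no grade record, and 2 of 9 reactors in Cohort A reach Grade 3 or higher: 2/9 = 22.2% against 2/18 = 11.1%.
4. If every subject has a record, m = 0 and the two bases agree.
5. In the by-visit table the full analysis set can itself mislead. With 9 of 18 subjects still attending and 5 reacting, the rate is 5/9 = 55.6% of those assessed but 5/18 = 27.8% of the set.

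**The case against.** The strongest reply is that little is lost. The worst-grade table covers the whole study, every reaction is listed, and the planned cohorts are 18 and 8. Grade 3 or higher reactions should also enter the adverse event tables. Stopping because of an intolerable reaction must be recorded in the eCRF (protocol 8.4.10), and adverse events leading to IMM-101 discontinuation are tabulated (SAP 5.15.1). A patient who attends a dosing visit but is not dosed may have the reaction recorded there. All analyses are descriptive. This stands, and it limits the weight of the point.

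A second reply is that the by-visit wording could mean reactions attributed to the dose given at that visit. That is possible, but 5.15.2 gives no rule for assigning a later assessment, including End of Study, back to a dose. Clarification is needed on either reading.

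A third reply is that the shells, a separate document not available here, may set another percentage base or add an End of Study column. That also stands. The SAP text remains the stated rule, and it differs from the protocol.

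A reader might infer that the tables as a whole lose the last-dose reaction and that the endpoint is miscounted. The documents do not support this. Only the by-visit table is affected, and the denominator rule changes percentages, not counts. A reader might also infer that the worst-grade table will divide by reactors only. The SAP does not say so: protocol 9.2.4 uses a 0 to 5 grading scale that covers these reactions, so a subject assessed with no reaction may well count as non-missing.

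**Conclusion.** Two narrow points hold.

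First, read literally, the by-visit reaction-type table has no place for the End of Study assessment. The omission is one post-dose assessment per subject: 4.5% of a completer's, a third after three doses, and the only one after a single dose. This assumes that the End of Study visit takes place (the protocol asks for it where possible) and that the last reaction was not already recorded at a dosing visit attended without a dose.

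Second, unless the shells say otherwise, the SAP's default base for these percentages is non-missing observations. That conflicts with protocol 11.1.1 and is not declared in SAP section 6. The effect is nil if every subject has a record, including those with no reaction. It could double a percentage if non-reactors are treated as missing and half the cohort reacts. The documents do not settle which applies. The objection carries most weight for the worst-grade table; for the by-visit table, the number assessed is the better base.

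Both are worth correcting: this is a named secondary endpoint, and protocol 18.3 identifies these reactions as the most notable risk across the IMM-101 studies.

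**What to change.** - **SAP 5.15.2, by-visit table:** summarise reaction type at each post-dose assessment, including the End of Study visit. Show the number of subjects assessed at each visit and use it as the base.
- **SAP 5.15.2, worst-grade-by-type table only:** use the Safety Analysis Set as denominator, with a 'no reaction' row.
- **SAP 5.1:** add the worst-grade table to the exceptions to the non-missing rule. Do not exempt all injection site reaction outputs, because that would put the full-set base on the by-visit table after dropout.
- **SAP section 6:** declare the by-visit base as a departure from protocol 11.1.1.
- **Shells:** check that they match.

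The cost is SAP wording, one extra visit column, a count of subjects assessed and one denominator. The protocol already schedules the assessments, so no new data collection is needed.

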5.15.3 Clinical Laboratory Evaluation

Observed values and change from baseline in haematology and biochemistry assessments will be summarised over time. If the test results are reported in categorical format, the results will be summarised by subject counts and percentage for each category.

Each haematology and biochemistry parameter will be classed as low, normal, high or missing based on the reference ranges. Shift tables in relation to the reference range from baseline over time will be presented.

Tables summarising clinical significance over time for haematology and biochemistry will also be presented.

Haematology and biochemistry data will be listed separately including change from baseline, reference ranges flagging all out of range values and their clinical significance.

Dipstick urinalysis and serology data will be listed only.

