## 6. SELECTION AND WITHDRAWAL OF PATIENTS

## 6.1 PATIENT INCLUSION CRITERIA

A patient must meet all of the following criteria to be eligible to participate in this study:

- 1. Patient must have a histologically-confirmed diagnosis of advanced (unresectable Stage III) or metastatic (Stage IV) melanoma excluding uveal/ocular melanoma. Patients with unknown primary melanoma are eligible
- 2. Patient has at least one measurable lesion by CT or MRI, according to RECIST 1.1.
- 3. Patient must have known BRAF V600 mutation status or consent to BRAF V600 mutation testing during the Screening Period.

- 4. Patients who have had prior radiotherapy must have been completed this at least 2 weeks prior to study drug administration (Week 0, Visit 1). Prior adjuvant or neoadjuvant melanoma therapy is permitted if it was completed at least 6 weeks prior to enrolment (Week 0, Visit 1), and all related adverse events have resolved or stabilised.
- 5. Patient is considered suitable for treatment with nivolumab.
- 6. Patient provides signed informed consent for participation in the study.
- 7. Patient has an Eastern Cooperative Oncology Group (ECOG)/World Health Organisation (WHO) Performance Status of ≤1 at Day 0.
- 8. Patient has Screening laboratory values meeting the following criteria. These should be obtained within 14 days prior to first dose on study:
  - Haemoglobin (Hb)  $\geq$ 9.0g/dL, absolute neutrophil count  $\geq$ 1.5 x 10^9/L, platelets  $\geq$ 100 x 10^9/L and White Blood Cells (WBC)  $\geq$  2.0 x 10^9/L (blood transfusion to achieve these levels are not permitted within 2 weeks of this assessment)
  - Total bilirubin ≤1.5 x upper limit of normal (ULN), excluding cases where elevated bilirubin can be attributed to Gilbert's Syndrome
  - Aspartate transaminase (AST; serum glutamic oxaloacetic transaminase [SGOT])
    and alanine transaminase (ALT; serum glutamate pyruvate transaminase [SGPT])
    each ≤2.5 x ULN or ≤5 x ULN in presence of liver metastases
  - Creatinine ≤1.5 x ULN
  - Serum albumin ≥30g/L
- 9. Patient is aged  $\geq$ 18 years.

For cohort A, the following inclusion criteria must also be met for a patient to be eligible to participate in this study:

- 1. Patient is treatment-naive (i.e., no prior systemic anticancer therapy for unresectable or metastatic melanoma).

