# 9.2.4 Intensity of Adverse Events

All AEs (or toxicities) including local injection site reactions encountered during the study will be evaluated according to the NCI CTCAE v4.03

[23] grading system (0 to 5), where applicable.

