### 11.1.4 Other Safety Endpoints

# Safety Laboratory Parameters

Laboratory parameter results will be summarised descriptively for continuous parameters, by assessment time point using summary statistics of actual values and change from baseline values. In addition, 'shift' tables of the number and percentage of patients with values outside normal range and within normal range at post baseline assessments by baseline assessment will be presented. Abnormal values will be flagged in data listings.

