2.2.2 Secondary Endpoints

The secondary efficacy endpoints of the study are:

- PFS assessed by RECIST 1.1 after a maximum of 18 months treatment in patients receiving IMM-101 + nivolumab.
- OS and OS at 1 year, for both cohort A and cohort B. The median OS (if applicable) and OS rate at 12 months will be estimated.

The secondary safety endpoints of the study are:

- Incidence and frequency of laboratory parameter abnormalities.
- Change from baseline values in laboratory parameter values.
- Incidence and frequency of local injection site reactions.

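### Laboratory shift tables use reference-range categories only, and no table counts patients by worst post-baseline CTCAE grade, so graded laboratory toxicity is tabulated only where it was reported as an AE

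*SAP*

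**What the plan says.** SAP 2.2.2 lists among the secondary safety endpoints: "Incidence and frequency of laboratory parameter abnormalities". SAP 5.15.3 then plans four kinds of output for haematology and biochemistry:

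- Continuous summaries: "Observed values and change from baseline in haematology and biochemistry assessments will be summarised over time". Under SAP 5.1, "Summary statistics for continuous variables will consist of the number of non-missing observations (n), mean, standard deviation (StD), minimum, median and maximum".
- Categories and shifts: "Each haematology and biochemistry parameter will be classed as low, normal, high or missing based on the reference ranges", followed by "Shift tables in relation to the reference range from baseline over time will be presented".
- Tables of clinical significance over time.
- Listings with change from baseline, reference ranges, out-of-range flags and clinical significance.

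Protocol 11.1.4 also asks for an ungraded shift table, giving the "number and percentage of patients with values outside normal range and within normal range at post baseline assessments by baseline assessment".

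Three other provisions bear on the point. Protocol 6.1, general criterion 8, admits patients with ALT and AST "each ≤2.5 x ULN or ≤5 x ULN in presence of liver metastases", and with bilirubin (Gilbert's Syndrome excepted) and creatinine up to 1.5 x ULN. SAP 5.4 restricts safety tables to scheduled post-baseline data, with repeat and unscheduled results listed only. Protocol 9.2.4 sets the toxicity scale: "All AEs (or toxicities) including local injection site reactions encountered during the study will be evaluated according to the NCI CTCAE v4.03", where applicable.

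**The concern.** A shift table on low, normal and high shows when a patient crosses a limit. It cannot show how far. That matters most for patients who are already outside the range at entry, whom this trial accepts. They have no further category to move into, so a large deterioration is displayed as no change.

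Safety of the combination is a primary objective, to be set against published data on nivolumab alone (Protocol 4), and Protocol 9.1 gives the six-monthly safety reviews a particular focus on immune-related events. For that purpose the useful figure is how many patients reached each severity of, for example, transaminase rise. The plan holds the numbers needed for that count but does not make it. SAP 5.15.2, the section just before, does plan a worst-CTCAE-grade summary over the whole study for injection site reactions, which are another secondary safety endpoint.

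**Working it through.** The plan states no figure on this point, so there is none to reproduce. The check is of the classification rule, then of whether another planned output supplies what the shift table lacks.

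**Step 1. The rule.** A value above ULN is *high*, whatever its size. The entry values 5 and 2.5 x ULN are the limits in Protocol 6.1. The normal baseline, set at 1.0 x ULN, and all follow-up values are illustrative assumptions. Change = later value minus entry value.

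| Entry (x ULN) | Later (x ULN) | Shift cell | Change (x ULN) |
|---|---|---|---|
| 5 (liver metastases) | 6 | high to high | 6 - 5 = +1 |
| 5 (liver metastases) | 10 | high to high | 10 - 5 = +5 |
| 5 (liver metastases) | 25 | high to high | 25 - 5 = +20 |
| 2.5 (no liver metastases) | 25 | high to high | 25 - 2.5 = +22.5 |
| 1.0 (normal) | 1.1 | normal to high | 1.1 - 1.0 = +0.1 |
| 1.0 (normal) | 25 | normal to high | 25 - 1.0 = +24 |

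Changes from +1 to +22.5 share one cell, and changes of +0.1 and +24 share another. Above ULN, the shift table carries no information on size. This does not depend on where CTCAE sets its cut-points, which the documents do not give.

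**Step 2. The other planned outputs.**

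| Output | What it shows | What it does not show |
|---|---|---|
| Observed values and change, by visit (SAP 5.15.3, 5.1) | An extreme value, through the minimum or maximum | How many patients reached a given severity; each patient's worst value; any unscheduled result |
| Clinical significance over time (SAP 5.15.3) | Abnormalities the investigator considered significant | Grade |
| Listings (SAP 5.15.3, 5.4) | Every value, unscheduled ones included | Any count |
| TEAEs by CTCAE grade, and Grade 3 or above by SOC and PT (SAP 5.15.1) | Grade | Results not reported as AEs |

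The last row depends on Protocol 9.4, under which abnormal results judged clinically significant are recorded as AEs. It is the only planned route from a laboratory value to a graded table.

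**Step 3. Unscheduled results.** Protocol Table 1 schedules safety bloods every 4 weeks from Week 12 to Week 76. A peak found on an extra sample between visits enters neither the shift table nor the visit maximum, because SAP 5.4 disregards such results in safety tables.

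**Step 4. Size.** With the planned enrolment (SAP 3), one patient is 1/18 = 5.6% of Cohort A and 1/8 = 12.5% of Cohort B. The share of patients entering above ULN is not given, so the number who could not show an upward shift cannot be calculated.

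**The case against.** The strongest answer is that severity is already covered. The example patient who goes from 5 to 25 x ULN would probably be the maximum in the observed-value and change summaries in a cohort of 18 or 8, would be flagged in the listings, and would very likely be called clinically significant. The event would then be an AE, graded by CTCAE v4.03, and would appear in the Grade 3 or above table and listing. Biochemistry and haematology are also reviewed every 6 months (Protocol 9.1). The endpoint's wording has no severity element, and SAP 5.15.3 delivers what Protocol 11.1.4 asks for, while also separating low from high and adding clinical significance. The study is descriptive, with full listings.

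Most of this stands, and it rules out several stronger readings:

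- A reader might infer that laboratory data are tabulated only as low, normal or high. They are not. The same SAP section tabulates values, change and clinical significance.
- A reader might infer that mild and severe toxicity cannot be told apart anywhere. That is true of the shift tables, not of the listings or of results reported as AEs.
- A reader might take 5 x ULN as the general entry limit. It applies only with liver metastases.
- A reader might see a conflict between the SAP and the protocol. There is none: both plan ungraded shift tables.

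What the objection leaves open is the patient count. Visit-level extremes are not an incidence, and the graded AE tables rest on the investigator's judgement in an open-label study although the numeric values are held.

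**Conclusion.** The point holds as a gap in tabulation, not a loss of data. The shift tables are blind to size beyond the reference limit. No planned table gives each patient's worst post-baseline grade, and unscheduled peaks are left out of the safety tables. Graded laboratory toxicity is therefore tabulated only where the result was judged clinically significant and reported as an AE.

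It is a cheap improvement, not a failure to meet an endpoint. Each misplaced patient counts for 5.6 percentage points in Cohort A or 12.5 in Cohort B at planned enrolment. No expected number of such patients is claimed, and nothing in the documents suggests that investigators would fail to report severe results.

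The conclusion rests on the SAP and protocol text. The table shells are a separate document (SAP 1) and were not available. If they already contain a worst-grade laboratory table, the point is met and only the SAP wording needs to catch up.

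**What to change.** In SAP 5.15.3 add, by cohort, a table of baseline grade against worst post-baseline CTCAE v4.03 grade for every laboratory parameter that this version grades numerically. Derive the grades from the recorded values and reference ranges, and show the number and percentage of patients worsening to Grade 3 or above.

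State that this table includes repeat and unscheduled results, as an explicit exception to SAP 5.4. Without that exception, a worst-grade table could miss the peaks it is meant to catch.

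Keep the reference-range shift tables for parameters without a numeric grade. The by-visit summaries, clinical-significance tables and listings can stay as they are.

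The cost is SAP and shell wording, some programming on values already collected, and one more table per panel. No new data are needed.
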